Brief Summary	
In this research, we will conduct a double-blind, sham-controlled, randomized trial to examine the impact on cardiometabolic biomarkers of air pollution exposure reduction using home portable air cleaners (PACs) in a cohort of current adult patients at NYU Langone Health. This study is funded by CTSI (NIH/NCATS UL1TR001445) with two primary aims and two secondary/exploratory aims. In Aim 1, we will evaluate associations with PAC use with a priori specified biomarker of inflammation, tumor necrosis factor alpha (TNFα). We will determine if 4 weeks of home air filtration with PACs compared to sham is associated with significant reductions in TNFα concentrations when measured before and after intervention. Blood samples will be collected from 44 study participants before and after 4 weeks of PAC use (true and sham) for biomarker concentration measurement. In Aim 2, we will determine if reductions in fine particulate matter (<2.5 μm in diameter, PM_{2.5}) as a continuous variable are associated with significant reductions TNFα concentrations over a four-week period. In Exploratory Aim 1, we will explore associations between PAC use and concentrations of cardiometabolic biomarkers using a targeted proteomic panel, the Olink Explore 384 Cardiometabolic panel, measured before and after 4 weeks of intervention. This will be a hypothesis-generating analysis to identify possible novel biomarkers and pathways that may have importance in the physiological responses and clinical outcomes associated with air pollution exposure. In Exploratory Aim 2, we will explore if biomarkers identified in Exploratory Aim 1 with significant reductions after 4 weeks of PAC partially mediate the association between reductions in PM_{2.5} and changes in daily home blood pressure (BP) measurements. Participants will be given home BP monitors to transmit de-identified daily morning BP measurements to a secure database during the 4 week intervention period. Changes in morning systolic (BP) will be analyzed as the outcome of interest, with changes in biomarker concentrations evaluated as a mediator of the relations between pollution reduction and changes in BP.

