Statistical Analysis	
For all Aims: descriptive summary statistics, such as mean and standard deviation (or median and inter quartile range) will be reported for continuous variables and counts and proportions for categorical variables. Graphical displays of all variables will be examined, with attention to assessing balance in these characteristics by intervention group, and with assessment of the distribution of variables, relevant to the choice of statistical tests. Statistical comparisons between the PAC and sham groups will be performed using a two-group two-sided t-test or nonparametric Wilcoxon test for continuous variables and Chi-square test for categorical variables. Distributions of biomarker concentrations will be examined and non-normally distributed concentrations will be log-transformed, as needed.
 
The analysis of our primary outcome for Aim 1 will use linear mixed-effects models with the change in prespecified biomarker, from pre-intervention to post-intervention, concentrations as the dependent variable and treatment arm as the independent variable. While randomization should obviate the need for additional adjustment, models will be adjusted for age, gender and BMI, as these are known to be related to inflammatory biomarker concentrations. These models use subject-specific random intercepts to account for heterogeneity between subjects and will account for within subject correlation between biomarker observations.
 
For Aim 2, we will also utilize similar models incorporating $PM_{2.5}$ as the independent variable. This will be assessed as the difference between pre-intervention baseline $PM_{2.5}$ concentration and the time-weighted average concentration of $PM_{2.5}$ from the 14-day intervention period.
 
For Exploratory Aim 1, we will evaluate the Olink panel results using mixed-effects models for the remaining biomarkers that were not prespecified. These will be the same models as for Aims 1 and 2, adjusted for age, gender, and BMI. For Exploratory Aim 2, we will evaluate associations of PAC use and $PM_{2.5}$ reduction with measured AM systolic blood pressure in this clinical cohort. We will perform mediation analysis using biomarkers with significant associations in Exploratory Aim 1 as mediators of the relations between $PM_{2.5}$ reduction and change in blood pressure.

Schematic of Study Design

1 Key Roles

Principal Investigator

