3.1 Primary Objective

The primary objective of this research is to examine the effectiveness of PAC use in improving inflammation related to cardiovascular disease.

Specific Aim 1: To determine if 4 weeks of home air filtration with PACs compared to sham is associated with significant reductions in TNF α concentrations when measured before and after intervention.

Specific Aim 2: To determine if reductions in PM $_{2.5}$ as a continuous variable are associated with significant reductions TNF α concentrations over a four-week period.

Exploratory Aim 1: To explore associations between PAC use and concentrations of cardiometabolic biomarkers using a targeted proteomic panel, the Olink Explore 384 Cardiometabolic panel, measured before and after 4 weeks of intervention.

Exploratory Aim 2: To explore if changes in TNF α and other novel cardiometabolic biomarkers partially mediate the effects of PACs on home blood pressure.

4 Study Design and Endpoints

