Exploratory Aim 2: To explore if changes in TNF α and other novel cardiometabolic biomarkers partially mediate the effects of PACs on home blood pressure. For this Aim, participants will monitor blood pressure daily during the 4-week intervention period using commercially available BP monitor with a paired data hub that transmits BP measurements to an online dashboard in real time. Participants will receive written and verbal instructions for proper BP recording technique at the baseline visit. They will record two measurements in a seated position each morning and evening during the study periods. The outcome of interest will be the mean of two AM systolic blood pressure measures. We will perform mediation analysis to analyze the direct and indirect effects of changes in significant biomarkers and PM_{2.5} changes on AM systolic BP. Based on our own pilot study of the effect of PAC use on AM systolic BP, we anticipate up to 30% missing BP measurements. We surveyed our prior pilot cohort regarding reasons for missing measurements and the predominant reported reason was forgetting; participants noted that they would have liked daily reminders. We will offer participants the option to receive daily text message reminders to record BP. These have been reported to be effective in other studies of home BP as well.

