We will also utilize similar models incorporating PM_{2.5} as the independent variable in place of PAC arm. This will be assessed as the difference between pre-intervention baseline PM_{2.5} concentration and the time-weighted average concentration of PM_{2.5} from the 14-day intervention period. For our exploratory aim we will evaluate the Olink panel results using mixed-effects models for the remaining biomarkers that were not prespecified. Additionally, we will explore associations of PAC use with measured blood pressure in this clinical cohort that likely differs from our current pilot cohort recruited from a community setting. Because this pilot will integrate with our larger R01 trial, for which blood pressure is the primary outcome of interest, we will incorporate this biomarker data into that trial for a secondary exploratory analysis of biomarkers as mediators in the association between PAC use and blood pressure reductions.

In our exploratory analysis, there will be multiple testing bias due to utilizing a panel of 369 possible biomarker outcomes. With this size pilot cohort, it will be unlikely to achieve statistical significance if strict adjustments for multiple testing are undertaken. However, we will use the Holm procedure to evaluate for significance. Overall, these exploratory analyses will be hypothesis-generating and can help inform the design and sample size of future cohorts.

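### Exploratory Aim 2 picks its panel mediators by significance after Holm over 369 proteins, so at 44 participants the panel-derived set may well be empty; no fallback is stated and the role of TNFα is inconsistent.

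*Combined protocol and SAP*

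**What the plan says.** Several places define the mediators for Exploratory Aim 2, and they differ.

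- Protocol Summary, Statistical Analysis: "We will perform mediation analysis using biomarkers with significant associations in Exploratory Aim 1 as mediators" of the relation between PM2.5 reduction and change in blood pressure.
- Protocol Summary, Brief Summary: the aim is to "explore if biomarkers identified in Exploratory Aim 1 with significant reductions after 4 weeks of PAC partially mediate the association" between PM2.5 reduction and home blood pressure.
- Protocol Summary, Objectives: mediators are novel biomarkers identified in Exploratory Aim 1, with no threshold stated.
- Section 3.1, and the aim sentence in section 4.1: "To explore if changes in TNF α and other novel cardiometabolic biomarkers partially mediate" the effect of PACs on home blood pressure. TNFα is named, and no significance condition is attached.
- The analysis sentence in section 4.1: the model concerns the "direct and indirect effects of changes in significant biomarkers" and PM2.5 changes on morning systolic pressure.

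On what counts as significant for the panel, section 10.3 says of its 369 outcomes: "With this size pilot cohort, it will be unlikely to achieve statistical significance if strict adjustments for multiple testing are undertaken". The next sentence reads: "However, we will use the Holm procedure to evaluate for significance". No other panel threshold appears, and nothing says what happens if no protein passes.

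**The concern.** The Protocol Summary and the analysis sentence in 4.1 let a panel protein into the mediation analysis only if it is significant in Exploratory Aim 1. Section 10.3 then sets a significance rule that it does not expect the cohort to satisfy. Holm can reject nothing unless the smallest p-value is at or below 0.05/369, so its first step is as strict as Bonferroni.

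A significant exposure-to-mediator test is not needed to estimate an indirect effect with an interval. The gate therefore withholds estimates without any technical need. If no protein passes, the pilot gives no mediator-to-BP path and no indirect effect for any panel protein, including the six singled out in sections 2.1 and 4.1. Those are quantities a later mediation study would want for planning, and informing later cohorts is the use that 10.3 gives for its exploratory analyses.

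Without a written fallback, a zero count also invites a later switch to unadjusted p < 0.05. With 369 tests and no true effect, that would be expected to yield 369 × 0.05 = 18.45 false mediators.

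**Working it through.** **Inputs from the documents.** Alpha 0.05; power above 80% at a sample size of 66; a 10% change; covariates age, BMI and gender; up to 10% dropout (10.4). Allocation 1:1 with 22 per arm (Protocol Summary). Panel of 369 (10.3). Enrolment of 74 with 90% completing (5.6; 74 also in 4.1).

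**Assumptions.** No SD, R² or standardised effect is stated, so the power figure cannot be checked forward and the effect is back-solved from it. The test is taken as two-sided. Affected proteins share one effect size and are independent.

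**Step 1: effect implied by the plan.** Power = P(|T| > t crit), with T noncentral t, df = n − 5 (intercept, arm, three covariates) and noncentrality λ = d√n/2.
- Solving for 80% at n = 66 and alpha 0.05 gives d = 0.70, an SD of 10/0.70 ≈ 14.3 percentage points for a 10% change.
- 66/0.90 = 73.3, which rounds up to 74 and matches 4.1 and 5.6, so 66 reads as completers. If only 60 of 66 were analysed, d would be 0.74.

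**Step 2: first Holm step.** 0.05/369 = 0.000136. Using 368 or 384 tests changes the per-protein power by at most about 0.2 percentage points.

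**Step 3: power per protein at d = 0.70, and chance of an empty set, (1 − power)^k.** The 40 is 44 × 0.9 = 39.6, rounded.

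| n analysed | λ | t crit | Power per protein | Empty, k = 6 | Empty, k = 20 |
|---|---|---|---|---|---|
| 40 | 2.22 | 4.29 | 3.4% | 81% | 50% |
| 44 | 2.32 | 4.23 | 4.4% | 76% | 40% |
| 66 | 2.85 | 4.07 | 12.8% | 44% | 6.5% |

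For example, at n = 40 and k = 6: (1 − 0.0343)^6 = 0.811.

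**Step 4: sensitivity, six affected proteins.**
- d = 0.74, n = 44: empty 71%.
- d = 0.5: power about 1% per protein; empty 94–95% (n = 44 and 40).
- d = 1.0: power 17–21%; empty 24–34% (n = 44 and 40).
- At d = 0.70, an even chance of at least one pass needs ln 0.5 / ln(1 − power): about 15 affected proteins at n = 44, or 20 at n = 40.

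Positive correlation between affected proteins makes an empty set more likely. False positives among unaffected proteins make it less likely, by at most 5 percentage points, because Holm caps that chance at 0.05.

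**Step 5: effect of TNFα.** TNFα is the prespecified Aim 1 biomarker, and the exploratory panel models cover the remaining ones, so it lies outside the Holm family.
- If TNFα is a mediator regardless of significance, as 3.1 reads, the overall mediator set is never empty.
- If TNFα must be significant at 0.05, its power at d = 0.70 is 58% (n = 40) or 62% (n = 44). With the six proteins and independence, the overall set is then empty 0.811 × (1 − 0.577) = 34% or 0.761 × (1 − 0.621) = 29% of the time.
- If mediators come only from Exploratory Aim 1, as the Protocol Summary reads, TNFα is not a candidate and Step 3 applies.

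**The case against.** A reader might infer that the whole aim cannot be carried out. The documents do not support that. The Protocol Summary places in Exploratory Aim 2 the associations of PAC use and PM2.5 reduction with morning systolic pressure, and the endpoint in 4.2.2 is change in that pressure as a function of PM2.5 change. Neither needs a mediator.

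A reader might also infer that mediation is confined to Holm-significant proteins. The Protocol Summary sentence does not mention Holm; the link comes from 10.3. Section 3.1 and the aim sentence in 4.1 name TNFα without a gate, so a TNFα model could be run.

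Nor would the pilot be left without path estimates. Exploratory Aim 1 fits exposure-to-protein models across the panel whatever the p-values. Section 10.3 also sends the biomarker data to a larger trial for a mediation analysis with no Holm gate stated, although that does not answer this pilot's own aim.

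The probability of an empty set rests on an unstated SD and an assumed number of affected proteins. If the 74 in 4.1 and 5.6 is the real target, about 66 would complete and a set drawn from six affected proteins would be more likely non-empty than empty. Finally, screening mediators is a legitimate choice in work labelled exploratory, and 10.3 is open about its limited power.

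All of this stands, and it limits the point to panel-derived mediators. It does not supply a fallback, and it does not tell the analyst whether a non-significant TNFα goes forward.

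**Conclusion.** The point holds for panel proteins. Their selection depends on significance, the only stated panel rule is Holm over 369, the plan itself calls significance unlikely, and no fallback exists. At the planned 44 participants and the effect implied by 10.4, an empty panel set is more likely than not unless about 15–20 independent proteins are truly affected or effects are well above the implied size; with six affected it is empty about 76–81% of the time. With 66 analysed the figure is about 44%. The results rest on the back-solved d of 0.70, a common effect size and independence.

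What would be lost is the mediator-to-BP path and the indirect effect for panel proteins. Separately, the sections contradict one another on TNFα: 3.1 and the aim sentence in 4.1 include it outright, while the Protocol Summary and the analysis sentence in 4.1 point to Exploratory Aim 1 or to significant biomarkers. This is worth correcting before analysis, at a weight suited to an exploratory aim.

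**What to change.** In the Protocol Summary (Statistical Analysis), section 4.1 (Exploratory Aim 2) and section 10.3:

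- Replace the significance gate with a prespecified mediator list: TNFα plus Angiopoietin-1, ICAM-1, VCAM-1, PCSK9, sP-selectin and BNP. Sections 2.1 and 4.1 name these six for association analyses, so their role as mediators must be written in.
- Estimate each indirect effect with a bootstrap 95% confidence interval, whatever its p-value in Exploratory Aim 1.
- Add any other panel protein that passes Holm, labelled as data-selected.
- Report everything as exploratory estimates, with no claim of mediation based on a p-value.
- Make the aim wording agree across the Brief Summary, Objectives and Statistical Analysis entries of the Protocol Summary and sections 3.1 and 4.1.

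The cost is wording and a few extra model fits on data already being collected. The downside is that the estimates will be imprecise, and some will concern proteins that PAC use does not change.

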10.4 Sample Size

Power Analysis: While we do not expect substantial participant dropout over this short trial, our power analyses include adjustment for up to 10% dropout in each arm. Based on our meta-analysis of biomarkers²², we estimate a 10% change in concentration of biomarkers with PAC use versus sham.^{13 13} Using a basic multiple regression model incorporating age, BMI, and gender, along with our exposure (active PAC vs sham), we will have greater than 80% power to reject the null hypothesis of zero effect size at the significance level (alpha) of 0.05, with a sample size of 66. As such, our enrollment goal of 44 participants, limited by budgetary constraints, may provide sufficient power to detect significant changes in biomarker concentrations. However, in the event that we are not able to reach statistical significance with the changes we detect, these results will still be informative for developing future studies. We will include baseline-only data for participants who do not complete the protocol.

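### Exploratory Aim 2 estimates mediation for proteins chosen by significance in the same participants, so selected effects will on average be too large and should not feed future sample sizes unadjusted

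*Combined protocol and SAP*

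**What the plan says.** The Protocol Summary (Statistical Analysis) plans "mediation analysis using biomarkers with significant associations in Exploratory Aim 1 as mediators" of the relation between PM2.5 reduction and blood pressure change. Its Brief Summary selects in the same way: the aim is to "explore if biomarkers identified in Exploratory Aim 1 with significant reductions after 4 weeks of PAC partially mediate" the PM2.5 to blood pressure association. Section 4.1 (Exploratory Aim 2) also refers to significant biomarkers. Section 3.1 is worded differently. It asks whether TNFα and "other novel cardiometabolic biomarkers partially mediate the effects of PACs on home blood pressure", with no significance filter in that sentence.

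The Protocol Summary does not define significant. Section 10.3 recognises multiple testing from "utilizing a panel of 369 possible biomarker outcomes", concedes that "it will be unlikely to achieve statistical significance if strict adjustments for multiple testing are undertaken", and then states that "we will use the Holm procedure to evaluate for significance". It calls these analyses hypothesis-generating and adds that they "can help inform the design and sample size of future cohorts". It also plans to carry the pilot biomarker data into a larger trial for a secondary mediation analysis.

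The plan has no sample split, shrinkage, selection-adjusted interval or independent replication before the selected proteins are estimated.

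**The concern.** When a protein enters the mediation analysis only because its estimated effect was large relative to its standard error, and that same estimate then forms the first leg of the indirect effect, the estimate is biased away from zero on average. The bias is worst where power is low, and a Holm threshold over 369 tests in a pilot of this size is a low-power setting.

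The mediation estimates could be reported at face value. They could also be used to plan a later study. Sample size varies with the inverse square of the standardised effect, so even modest inflation would leave a follow-up well short.

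**Working it through.** **Inputs from the documents**
- Planned effect: 10% change versus sham; power above 80% "at the significance level (alpha) of 0.05, with a sample size of 66" (10.4).
- Enrolment: 44 (Protocol Summary, 5.4, 10.4) or 74 (4.1, 5.6). Dropout up to 10% (10.4); 90% expected to complete (5.6).
- Allocation 1:1; 369 proteins; Holm (10.3).
- Model: arm, age, gender, BMI and an intercept, so residual df = N − 5.

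**Assumptions.** The SD of change is not given, so the true d is back-solved and then varied. Tests are two-sided.

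**Step 1: the plan's own figure.** The N = 66 statement cannot be reproduced without an SD; it can only be inverted. The standard error of a standardised arm difference is 2/√N.
- Normal approximation: d = (1.960 + 0.842) × 2/√66 = 0.69. With the noncentral t on 61 df, d = 0.70.
- Implied SD of change: 10/0.70 = 14.3 percentage points.
- 66/0.9 = 73.3, rounded up to 74, matches the enrolment in 4.1 and 5.6, so 66 is read as completers. If 66 already included dropout (about 60 analysed), d would be 0.74.

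**Step 2: completers.** 44 × 0.9 = 39.6, about 40. 74 × 0.9 = 66.6, about 67.

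**Step 3: the bar a protein must clear.** First Holm step: 0.05/369 = 0.0001355. At N = 40 (35 df) this needs |t| > 4.29, so the observed standardised difference must be at least 4.286 × 2/√40 = 1.355. The implied planning effect is 0.70.

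**Step 4: what passing does to the estimate.** I drew the estimate as d + (2/√N)·z and the SD ratio as s = √(χ²/df), 4 million draws per setting, and kept draws whose |t| exceeded the threshold. Inflation is the mean of |estimate| divided by d. Coverage is the share of ordinary 95% intervals that contain d.

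| True d | N=40 Holm: passes | inflation | coverage | N=67 Holm: inflation | coverage | N=40, p<0.05: inflation | coverage |
|---|---|---|---|---|---|---|---|
| 0.3 | 0.16% | 4.1 | 0% | 3.3 | 0% | 2.6 | 82% |
| 0.5 | 0.8% | 2.55 | 1% | 2.05 | 23% | 1.7 | 93% |
| 0.7 | 3.4% | 1.90 | 34% | 1.53 | 81% | 1.3 | 96% |
| 0.9 | 10% | 1.55 | 76% | 1.26 | 93% | 1.1 | 97% |
| 1.2 | 34% | 1.25 | 93% | 1.07 | 97% | 1.02 | 97% |

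For scale, at an SD of 14.3 the 7% (CRP) and 13% (IL-6) effects quoted in 2.1 are d of about 0.5 and 0.9.

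**Step 5: the mediated effect.** The indirect effect is a × b, with a the arm-to-protein path and b the protein-to-BP slope. Selection acts on a. With assumed b of 0.3 or 0.6 (standardised) and an assumed direct effect of 0.3, at N = 40, the Holm first step and d = 0.70, the product is also inflated about 1.9 times. Its Monte Carlo 95% interval covers the truth 87% (b = 0.3) or 75% (b = 0.6) of the time, because uncertainty in b widens it. At d = 0.5 coverage is 83% or 61%; at d = 0.3 it is 80% or 39%.

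**Step 6: if the observed effect were used for planning.** At N = 40, Holm and d = 0.70 the standardised effect (estimate over estimated SD) is inflated 2.17 times. A study sized on it would be 2.17² = 4.7 times too small. The corresponding figures are 2.6 times at N = 67 and 1.8 times at N = 40 with p < 0.05.

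**The case against.** The strongest reply is that the plan is candid. Section 10.3 calls the analyses hypothesis-generating, expects few or no proteins to pass, and points to a further mediation analysis in a larger trial. It says only that the results can help inform future sample sizes, and an SD of change does that without harm. This stands as a reason for low severity. It does not remove the bias: the label corrects no estimate, and the larger trial would absorb the pilot data, so it is not described as an independent replication.

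A reader might infer three stronger things that the documents do not support:
- *Any protein that passes will be roughly doubled.* The 1.9 is an average under one back-solved effect, one of two enrolment figures and the Holm threshold. If many proteins passed, that would point to larger true effects and smaller inflation.
- *The mediation intervals mostly miss the truth.* The one-third coverage belongs to the arm-to-protein difference. At d = 0.70 the interval for the mediated effect covers 75–87% of the time under the assumed slopes.
- *Future trials will be powered on the observed effects of significant proteins.* Nothing says so; the 4.7 in Step 6 is conditional on that use.

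Two limits also apply. The quoted mediation sentence uses PM2.5 reduction as the exposure, and Exploratory Aim 1 follows the models of both Aims 1 and 2, so selection could be on arm or on PM2.5. Only the two-arm version is quantified here. The proportion mediated is not quantified either: its denominator, the total effect, also rises when path a is inflated, so the factor for a cannot be carried over. TNFα is prespecified and is not affected by this selection.

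**Conclusion.** The concern holds in a limited form. Selection and estimation share the same participants, no correction is planned, and the direction of the average bias does not depend on the assumptions. Its size does. The central figure (1.9-fold, about one third coverage for the arm-to-protein path) needs d of about 0.70, about 40 completers and the first Holm step. Inflation spans 1.25 to 4.1 for d from 1.2 to 0.3 at that N. At d = 0.70 it falls to about 1.5 with 81% coverage if 67 complete, and to 1.3 with 96% coverage under unadjusted p < 0.05. The mediated effect shares the inflation, with interval coverage only moderately below nominal at d = 0.70. Given the hypothesis-generating aim, this is a cheap improvement worth considering; the primary analysis is not affected.

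**What to change.** In 10.3:
1. Report empirical-Bayes shrunken effects for all panel proteins next to the raw ones, whether or not they pass Holm.
2. Label the mediation estimates of selected proteins as selection-biased, or give selection-conditional intervals for the exposure-to-protein path.
3. State that future sample sizes will use the SD of change and the shrunken effects, not the observed effects of significant proteins.

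Re-running the selection inside each bootstrap resample is not a substitute. Simulated for the arm-to-protein path with 20 per arm and d = 0.70, keeping only passing resamples gave about 0% coverage. Scoring the others as zero gave 97–98%, but only because about 30% of resamples were zeros, so the interval always reached zero.

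The cost is SAP wording and a little more analysis code, with no added participants, visits or assays. The downside is smaller, less striking effects, and a few true signals may be over-shrunk.
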